Procedures. Participants will first be asked questions about their mental health needs, challenges they face accessing care, and strategies they have used to manage their mental health. All participants will then be shown App Store descriptions of ten apps that have received the highest rating by PsyberGuide, a non-profit company that consistently rates existing apps for their safety, data privacy and user ratings. Participants will provide initial impressions on the acceptability and feasibility of using these apps. We will then ask participants if they would be willing to participate in a randomized trial to test these apps, with the aim of recruiting 1000 participants. Participants will be randomized (100 per group) to one of the ten apps. They will be asked to download their assigned app and use it for 4 weeks. We selected four weeks because (1) this is ample time to determine the usability, acceptability and feasibility of these apps (2) based on past remote research, this is when we will see the first effects of apps on mental health outcomes and (3) also based on past research, this is the longest period of time we will be able to maintain a 100-80% of the

sample. After 4 weeks of use, participants will be asked to provide an evaluation of acceptability, feasibility and usability of the app, how often they used the app, and if they found the app helpful. They will also complete PHQ9, GAD7, and brief Difficulties with Emotion Regulation Scale (DERS) and four measures from the IMV model of suicidal behavior – defeat, entrapment, thwarted belongingness, and perceived burdensomeness. The Suicidal Behaviors Questionnaire-Revised (SBQ-R), a four-item self-report that assesses suicide attempts, ideation, communication, and intent since the last assessment. Given some limitations of the attempt item in the SBQ-R (which is combined with suicidal ideation), an additional item "Have you attempted to kill yourself?" will be added. This single-item has been demonstrated to identify a research rated suicide attempt in 89.3% of cases. We will also ask if they used any other mental health apps or services during this 4-week period.

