T-tests and chi-square tests will compare demographic and baseline clinical outcomes by missing data status at follow-up timepoint. Chi-square tests will examine the association between condition assignment and compliance (whether a participant used the app they were assigned to or used an alternative app). All analyses are intent-to-treat. Sensitivity analyses will be conducted excluding those who never downloaded or used the app they were assigned. Analyses of variance will be used to compare conditions on AIM, IAM, and IUS scores at follow-up. A series of mixed effects models using restricted maximum likelihood estimation will be built to test linear time change on the PHQ-9, GAD-7, and DERS-SF, and to test for condition differences at follow-up and change slope. Models will be built in an outwardly nested fashion, such that an initial null model was computed, followed by models that add a random intercept, random time component, condition assignment, and condition x time interaction effects. To test whether there was a dose-response relationship such that the app use frequency was associated with rate of change on PHQ-9, GAD-7, and DERS-SF scores, we will compute another series of mixed effects models for each outcome. An initial model will include variables for time and frequency of use, a second model will add condition terms for each app using Beautiful Mind as reference, a third model will add condition x frequency interaction terms for each app, and the fourth model will include time, frequency, and a time x frequency interaction term. Model comparisons will apply -2 Log Likelihood, Akaike Information Criterion, and Bayesian Information deviance statistics. To test the impact of app use frequency on change over time, similar nested model testing will be applied using an initial null model, followed by models that added dosage, dosage x time interaction, and condition assignment.

Sample Size and Power. A priori power analysis for an ANOVA *F* test indicated that a sample size of 1,000 (n=200 participants in each of the active and control app conditions) would be sufficient with a power of .80 and an alpha of .05 for a minimum detectable effect size (MDES) of Cohen's d=.24 for main effect comparisons between any two conditions.

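### The app-specific dose terms (condition x frequency) are not crossed with time, so they dilute a dose-response on change and mix in pre-use severity

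*Combined protocol and SAP*

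**What the plan says.** The Analysis section sets out the dose question as whether "the app use frequency was associated with rate of change on PHQ-9, GAD-7, and DERS-SF scores". Four models follow.

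- Models 1 and 2: "An initial model will include variables for time and frequency of use, a second model will add condition terms for each app", with one named app as reference.
- Model 3: "a third model will add condition x frequency interaction terms for each app".
- Model 4: "the fourth model will include time, frequency, and a time x frequency interaction term". No condition terms are listed.

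A second dose series starts from a null model, "followed by models that added dosage, dosage x time interaction, and condition assignment".

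Three design facts matter.

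- There is one baseline and one follow-up; the attrition check will "compare demographic and baseline clinical outcomes by missing data status at follow-up timepoint".
- Use is asked once, after the 4 weeks (Procedures), when participants report "how often they used the app, and if they found the app helpful". It is therefore one value per person, observed after randomisation.
- On allocation, Procedures says "Participants will be randomized (100 per group) to one of the ten apps", whereas Sample Size and Power has 200 per condition in a total of 1,000.

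**The concern.** The question is about change, but the one model that allows the dose relation to vary by app has no dose term crossed with time. Condition x frequency x time appears in neither dose series. A frequency that is constant within person and not crossed with time can only explain a person's average level over the two occasions, and one of those occasions precedes any use of the app.

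Two consequences follow. A real app-specific dose-response on change enters diluted. Any between-app difference in how baseline severity relates to later use enters undiluted. The plan asks which apps reduce symptoms (Aim 1, Question 3) and foresees rapid dissemination, so an app-specific dose result that does not measure change could be misunderstood.

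**Working it through.** The plan gives no power or effect figure for the dose terms, so there is none to reproduce. Its sample-size statement concerns comparisons between conditions and is used here only for group size.

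**1. What model 3 estimates.** For a given app, let g be the slope of the baseline score on frequency and b the slope of change on frequency. The week-4 slope is then g + b. With a random intercept, equal variances and both occasions observed, the condition x frequency term compares slopes for the mean of the two scores:

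model-3 term = Δg + Δb/2, where Δ is app minus reference.

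Fitting the model by REML to simulated data (10 apps x 100, two occasions) confirmed this. Three model-3 coefficients (-0.6036, -2.3863, -0.6109) equalled those from ordinary regression of the two-occasion mean. The matching three-way terms (-1.2175, 0.1521, 0.8813) equalled those from regression of change.

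**2. How firm the half is.** If the model lets the two variances differ (SD ratio 0.8 to 1.2, correlation 0.4 to 0.6, assumed), the baseline weight runs from about 0.24 to 0.72. The share of Δb that gets through is then 0.76 to 0.28. People without follow-up have no reported frequency and so drop out of the model.

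**3. Dilution and power.** Assumed inputs, none from the documents: outcome SD 6, correlation ρ = 0.6, use SD 1.5, true app-specific effect δ = -1 point per unit of use, no baseline link. There are 80 responders per arm (100 per group at 80% retention, the low end of the range in Procedures). The residual variances are:

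- two-occasion mean: 36 x (1 + 0.6)/2 = 28.8
- change: 36 x 2 x (1 - 0.6) = 28.8
- week 4 given baseline: 36 x (1 - 0.36) = 23.04

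The SE of a slope difference is √(2 x variance / (80 x 1.5²)), which gives 0.566, 0.566 and 0.506. At two-sided 5%:

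| Term | Mean estimate | Estimate/SE | Power |
|---|---|---|---|
| Model 3 | -0.5 | 0.88 | 14% |
| Three-way (change) | -1.0 | 1.77 | 42% |
| Baseline-adjusted | -1.0 | 1.98 | 51% |

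Simulation agrees: 14% for model 3, against 41% (change) to 49% (baseline-adjusted). With 160 responders (200 per condition at 80%) the SEs are 0.400, 0.400 and 0.358, and power is 24%, 70% and 80%.

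**4. When the baseline link differs between apps.** Let Δr be the gap in the correlation of baseline severity with use. Then Δg = Δr x 6/1.5 = 4Δr. Regression to the mean carries 0.6 of that to week 4, so it contributes -(1 - 0.6) x 4Δr = -1.6Δr to Δb. Hence

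model-3 term = 4Δr + (δ - 1.6Δr)/2 = 3.2Δr + δ/2.

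| Δr | δ = 0 | δ = -1 |
|---|---|---|
| 0 | 0 | -0.50 |
| 0.10 | +0.32 | -0.18 |
| 0.15 | +0.48 | -0.02 |
| 0.30 | +0.96 | +0.46 |

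The expected sign reverses when Δr exceeds 0.5/3.2 = 0.156. In general the threshold is |δ| x 1.5/(6 x (1 + ρ)), which is 0.078 for δ = -0.5 and 0.313 for δ = -2. At Δr = 0.30 with no dose effect, model 3 is significant in about 40% of simulated trials. With δ = -1 as well, the estimate has the wrong sign in about 80% and is significantly wrong in about 12%.

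**5. The two candidate repairs are not equivalent.** At Δr = 0.30 and δ = 0, the three-way change term averages -1.6 x 0.30 = -0.48 and is significant in about 12-15% of simulated trials, an apparent benefit of use that is only regression to the mean. The baseline-adjusted term averages about 0 and is significant in about 5-6%. With δ = -1 the averages are -1.48 and -1.00.

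**The case against.** The strongest reply is that the stated dose question is tested on change: model 4 has time x frequency, and the second series has dosage x time. That stands for the dose relation pooled over apps. App-specific dose-response is not among Questions 1 to 3, and app differences in change are covered by the condition x time term of the main series. The gap is therefore confined to the app-specific dose terms in a secondary, observational analysis.

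Model 3 might also be defended as a mere nesting step. But model 4 as listed carries no condition terms, and even if they were kept, no later model adds the three-way term. Nor does coding frequency as 0 at baseline rescue it: with two occasions, frequency and time x frequency in model 4 would then be collinear.

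A reader might infer that model 3 will mainly show which apps sicker people use more, or that advice on use would come out reversed. The documents do not support that. It requires the severity-use link to differ between randomised apps, and nothing in the plan indicates by how much, or whether, it would. If the link is the same in every app, the sign is preserved and only dilution remains. Nor does the plan say that these terms will become advice on how much to use a given app.

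**Conclusion.** The concern holds in limited form. The app-specific dose terms do not measure app differences in dose-response on change, and no other listed model does. The near-certain consequence is dilution: about half the true effect, exactly half only under the conditions in step 1, with power of about 14% against 41-49% in the illustrative setting. A false signal or wrong sign is possible but conditional on the severity-use correlation differing between apps; for a -1 point effect, reversal needs a gap above roughly 0.15 in the opposing direction. Every SD, correlation and effect size here is assumed, and group size depends on which allocation statement applies. The pooled dose tests are not affected by this point. The change is worth making but does not touch the main comparison of apps.

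**What to change.** Replace the model-3 test, for each outcome, with a regression among those with follow-up of the week-4 score on baseline score, condition, frequency and condition x frequency. Read the joint interaction test before any single app. Its degrees of freedom are the number of conditions minus 1: 9 with ten apps, or 4 if 200 per condition in 1,000 means five conditions (1,000/200 = 5). The two allocation statements need to be aligned first.

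Condition x frequency x time with all lower-order terms may be reported as a supporting analysis. The text should say that it is not equivalent, because it keeps regression to the mean when use depends on baseline severity. Results should be described as associations, since use is self-selected and not randomised.

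The cost is analysis wording only, on data already planned. The downside is more model terms and modest power for single apps (about half for a -1 point effect at 80 responders per arm), so many app-specific results will be inconclusive.

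### No dose-response model holds condition × time together with time × frequency, so app differences in both use and change can pass for a dose-response

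*Combined protocol and SAP*

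**What the plan says.** The Analysis section (combined protocol and SAP) plans three sets of mixed models for the PHQ-9, GAD-7 and DERS-SF.

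- **Outcome series.** It compares the apps, and its last two steps are "condition assignment, and condition x time interaction effects". It contains no use variable. It is introduced as "A series of mixed effects models using restricted maximum likelihood estimation".
- **First dose series.** Its purpose is to test "whether there was a dose-response relationship such that the app use frequency was associated with rate of change". It starts simply: "An initial model will include variables for time and frequency of use". App main effects come next, then "a third model will add condition x frequency interaction terms for each app". For the last step, "the fourth model will include time, frequency, and a time x frequency interaction term".
- **Second dose series.** It starts from a null model, "followed by models that added dosage, dosage x time interaction, and condition assignment".

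Under Procedures, use is recorded at the four-week assessment, where participants report "how often they used the app, and if they found the app helpful". The Analysis section refers to baseline clinical measures and one follow-up, so there are two occasions.

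**The concern.** A link between use and rate of change can arise in two ways. Within an app, people who use it more may change more. Across apps, those that are used more may also be those whose users change more, for reasons unrelated to how much any one person uses them. Only the first supports a statement that using an app more goes with more improvement. Separating the two requires each app to have its own rate of change, which is the condition × time term.

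The plan clearly means to allow for app, because it puts app terms into both dose series. Those terms adjust the level of the outcome, not its change. A reader would take the dose-response result as adjusted for app when, for rate of change, it is not. If apps with more use happen to show less change, the same flaw can hide or reverse a real association. The findings are meant for rapid dissemination, so this distinction affects what users would be told.

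**Working it through.** **1. Terms in each planned model**

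| Model | Terms listed | time × frequency | condition × time |
|---|---|---|---|
| Outcome series, last step | time, condition, condition × time | no | yes |
| Dose model 1 | time, frequency | no | no |
| Dose model 2 | adds condition | no | no |
| Dose model 3 | adds condition × frequency | no | no |
| Dose model 4 | time, frequency, time × frequency | yes | no |
| Second dose series, last step | dosage, dosage × time, condition | yes | no |

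No row has both. Reading model 4 as cumulative on model 3 adds condition and condition × frequency, but still not condition × time.

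**2. Why the listed app terms do not help**

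Let F be reported use and D the follow-up score minus the baseline score. With two occasions, model 4 implies D = τ + βF + error, where β is the time × frequency coefficient. Condition and condition × frequency take the same value at both occasions for a given person, so they cancel in D. With or without them, β is estimated by Cov(F, D)/Var(F) over all participants. Condition × time replaces the single τ by one per app, and β becomes the within-app slope. Anyone without follow-up has no use value, so these models rest on people with both occasions.

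Scale use and change so that their within-app SDs are 1. Let s_u and s_c be the SDs of the app means and ρ their correlation across apps. With no within-app effect, the pooled slope is

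β = ρ · s_u · s_c / (s_u² + 1).

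For example, with ρ = .5:

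- s_u = .3, s_c = .1: .5 × .3 × .1 / 1.09 = .014
- s_u = .5, s_c = .2: .5 × .5 × .2 / 1.25 = .040
- s_u = .7, s_c = .3: .5 × .7 × .3 / 1.49 = .070

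The formula treats the number of apps as large. With ten apps the simulated means are a little lower: .013–.020 at s_c = .1, and at most .063 in the most extreme setting.

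*Check with fitted mixed models* (random intercept, REML, 60 simulated datasets, ten apps × 80, s_u = .5, s_c = .2, app use and app change perfectly correlated). The formula gives −.5 × .2 / 1.25 = −.080. Model 4 as written, model 4 read cumulatively, and the last model of the second series all gave a mean of −.083 and 77% rejection. Adding condition × time gave −.005 and 7%. In three further datasets fitted by ML at ρ = .5, the estimate was again the same to four decimals until condition × time was added.

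**3. Rejection rates**

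Inputs from the documents: ten apps, 100 per group and the lower retention figure of 80% (Procedures), so 100 × .80 = 80 per app; alpha .05 (Sample Size and Power), taken as two-sided. Assumed, because the documents give nothing: s_u, s_c and ρ. The true within-app effect is zero. There were 6,000 simulated trials per setting, regressing change on use.

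Rejection without condition × time, for s_u = .3 / .5 / .7:

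| s_c | ρ = 0 | ρ = .5 |
|---|---|---|
| 0 | 4.8 / 5.0 / 4.5% | – |
| .1 | 5.8 / 6.9 / 7.2% | 7.7 / 11.0 / 14.3% |
| .2 | 8.1 / 11.6 / 15.3% | 14.5 / 25.6 / 34.4% |
| .3 | 10.7 / 17.8 / 26.2% | 23.6 / 40.7 / 51.4% |

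With condition × time: 4.3–5.3% throughout. At ρ = 0 the slope averages zero, but with few apps chance alignment makes it vary more than its standard error allows.

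The power paragraph gives 200 per condition in 1,000, which implies five arms. With five arms × 160 and ρ = 0, the rates are 5.6–10.3%, 9.6–21.0% and 14.8–32.8% at s_c = .1, .2 and .3, against 4.6–5.4% within app.

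**4. Scale of the assumed app differences**

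The expected best-to-worst gap across ten normally distributed app means is about 3.08 SDs, so s_c = .1 corresponds to 3.08 × .1 = .31 SD. A gap equal to the plan's minimum detectable effect of .24 corresponds to s_c = .24 / 3.08 = .078. There the rates are 6–7% at ρ = 0 and 7–11% at ρ = .5.

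**The case against.** **The plan asks about an association, and model 4 tests one.** If well-used apps also show more change, the pooled association is real, and rejecting is an error only for a within-app claim. This stands as a point about the estimand, and it applies to every ρ = .5 figure above. It is a reason to keep the pooled estimate, labelled. It does not explain app terms that leave the tested coefficient untouched.

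**The size is assumed.** True. The larger rates need gaps of about .62 SD (s_c = .2) or .92 SD (s_c = .3), which are 2.6 and 3.8 times .24. Near .24 the inflation is modest.

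**Adjustment leaves self-selection.** Also true. Use is chosen after randomisation and self-reported at the same assessment as the outcome. Condition × time removes the between-app part only.

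**The second series may be shorthand.** It is described as similar to earlier nested testing, which could be meant to bring in condition × time. But the outcome series names condition and condition × time as separate steps, and the second dose series lists only the former. The text does not supply the term.

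**It is secondary.** Dose-response is not among the Aim 1 questions, and the randomised comparison already includes condition × time. This limits the weight of the point but does not answer it.

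**Conclusion.** The concern holds. That the term is missing, and that the listed app terms cannot affect the time × frequency estimate, follows from the text and from having two occasions with a single report of use; neither depends on assumed values. How much it matters does depend on them. There is no inflation if apps differ only in use or only in change. It is slight when app differences are near the plan's own detectable effect and unrelated to use, and substantial when the more-used apps also change more. The point affects a secondary, observational analysis. It is worth correcting because the change is cheap and makes the plan's intended allowance for app work on the question it poses.

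**What to change.** - Define the dose-response test as the addition of time × frequency to a model containing time, condition, condition × time and frequency.
- Fit both models by maximum likelihood for that comparison. REML likelihoods are not comparable between models with different fixed effects. REML is the only estimator the Analysis section names, and it names none for the dose series. This is a separate point, but it belongs in the same sentence of the SAP.
- Report the model without condition × time alongside, labelled as a pooled estimate that mixes within-app and between-app differences.
- Describe the adjusted result as a within-app observational association, not as an effect of use.

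The cost is SAP wording, with no new data. With ten apps it adds 10 − 1 = 9 fixed-effect terms to the last model of the second series. The standard error of the dose coefficient was about 1–19% larger in the ten-app settings (ratio 1.006–1.192). The adjusted estimate excludes any genuine between-app dose effect, which is why the pooled one should stay beside it.

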Question 1: Which mental health apps will be deemed to be acceptable (Acceptability of Intervention Measure), Feasible (Intervention Feasibility Measure), and Usable (Intervention Usability Measure) by essential workers and the unemployed?

Question 2: What features of these interventions did participants find particularly helpful?

Question 3: Which apps result in reduced depression (PHQ-9), anxiety (GAD-7) and better emotional regulation (DERS)?

Aim 2: To disseminate our findings and recommendations through national partnerships, the UWAC website, the ALACRITY Centers network, CSPAR and suicide prevention organizations, and WA state DPH.

Methods

Participants. Participants will be recruited in three ways: (1) mTurk; (2) MHA ads; and (3) Facebook Ads. We will aim to recruit 2,000 participants over the course of one week. Based on our past research, this sample is feasible to recruit in our proposed time frame. We have been able to recruit samples larger than this in 3 weeks using all of these methods. Participants will be eligible if (1) they are an essential worker or unemployed due to COVID19; (2) they have a past history of mental health issues or experiencing suicide ideation motivational risk factors based on the Integrated Motivational-Volitional (IMV) Model of Suicidal Behaviour. Participants will be compensated for their participation in this study.

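### Models fitted by REML that differ in fixed effects are, on the natural reading, compared by -2LL, AIC and BIC, which is not valid, and no deciding test is named

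*Combined protocol and SAP*

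**What the plan says.** The Analysis section names an estimator for one set of models only: "A series of mixed effects models using restricted maximum likelihood estimation will be built to test linear time change" on the three symptom scales, and "to test for condition differences at follow-up and change slope". The series starts from a null model, "followed by models that add a random intercept, random time component, condition assignment, and condition x time interaction effects". The first two additions are random effects. The last two are fixed effects, with 9 parameters each for the ten apps of the Procedures section, or 4 each for the five conditions implied by a total of 1,000 with "n=200 participants in each of the active and control app conditions" (Sample Size and Power).

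A dose-response series follows. Its estimator is not named, and it too changes fixed effects from model to model. Then comes the only comparison rule in the document: "Model comparisons will apply -2 Log Likelihood, Akaike Information Criterion, and Bayesian Information deviance statistics". The next sentence, on app-use frequency and change over time, says that "similar nested model testing will be applied using an initial null model".

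The document never mentions ML. For the condition terms it names no likelihood-ratio, F, Wald or coefficient test, and it does not say what happens when the three statistics disagree. The .05 alpha appears only in the power paragraph, for an ANOVA F test.

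**The concern.** REML uses the likelihood of the data after the fixed effects have been removed. Two models with different fixed effects therefore have likelihoods for different transformed data. Their -2LL, AIC and BIC cannot be subtracted meaningfully, and the difference depends on units that carry no information about the apps.

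Question 3 of Aim 1, which asks which apps improve the three scales, is what is at stake. To the extent that the deviance comparisons decide whether apps differ, their false-positive rate and power vary with each scale's SD, with the form of REML that the software reports and, for condition x time in one of those forms, with the unit of time.

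Three things are not at stake: the ANOVAs for Question 1; coefficient, F or Wald tests taken from a REML fit; and REML comparisons of the random-effect steps when the fixed effects are the same.

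**Working it through.** **Inputs.** From the plan: REML; the order of the steps; ten apps x 100 (Procedures) or 200 per condition in 1,000 (Sample Size and Power); 4 weeks of use; d=.24. Assumed, because the plan gives no value: SD 5 (also 4 and 6), correlation .6 between the two waves, complete data, random intercept only, dummy coding of condition.

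**The plan's own figure.** The plan gives none for this comparison. Its d=.24 serves below only as an effect size. It is not reproduced by the two-sided formula, (1.960 + 0.842) x sqrt(2/200) = 0.280; that is a separate matter, and nothing here depends on it.

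**Exact shifts.** Let q be the number of fixed-effect parameters added (9 or 4).

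- Multiplying the outcome by c adds 2(N - p) ln c to the REML -2LL of a model with N records and p fixed effects. The difference between the two models therefore moves by 2q ln c. Doubling gives 18 ln 2 = 12.48 (ten arms) or 8 ln 2 = 5.55 (five arms). For SD 6 against SD 4 with the same standardised data it is 18 ln 1.5 = 7.30 or 8 ln 1.5 = 3.24.
- In the REML form that omits log|X'X|, coding time 0/4 instead of 0/1 multiplies the q interaction columns by 4. The condition x time difference falls by 18 ln 4 = 24.95 or 8 ln 4 = 11.09.
- Under ML both shifts are 0.

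**One simulated dataset** (ten arms x 100, no true effect), fitted with a standard mixed-model package. The condition x time difference in -2LL under ML is 9.71 in every case. Under REML it is 13.72 with time 0/1, 26.20 with the outcome doubled (+12.48) and -11.23 with time 0/4 (-24.95).

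**Illustration** (4,000 runs per scenario, Monte Carlo SE at most 0.8 points, form omitting log|X'X|). AIC chooses the larger model when the -2LL difference exceeds 2q, that is 18 or 8.

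| AIC chooses condition x time | ML | REML, time 0/1 | REML, time 0/4 |
|---|---|---|---|
| Ten arms, no true effect | 3.8% | 14.1% | 0% |
| Ten arms, five apps better by d=.24 | 81.8% | 93.8% | 11.3% |
| Five arms, no true effect | 9.0% | 7.8% | 0.1% |
| Five arms, three apps better by d=.24 | 96.1% | 95.6% | 54.3% |

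A large-sample formula explains the pattern. With k arms of n, time 0/1 and residual variance s2 = SD^2 (1 - r), the REML difference exceeds the ML difference by q ln(2 pi) - q ln[n/(2 s2)] + ln k.

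- Ten arms, s2 = 25 x .4 = 10: 9(1.838) - 9 ln 5 + ln 10 = 4.36, hence the inflation.
- Five arms: 4(1.838) - 4 ln 10 + ln 5 = -0.25, hence little or none.
- Ten arms at SD 4 (s2 = 6.4): 0.34. At SD 6 (s2 = 14.4): 7.64. The gap is the 7.30 above, and simulated null selection is 3.9% and 30.9%.

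In the form that keeps log|X'X|, time coding no longer matters, but AIC chose the null interaction in every run (mean difference 46.2 with ten arms, 20.5 with five).

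**No deciding rule.** Counting persons, BIC needs a difference above 9 ln 1000 = 62.2 or 4 ln 1000 = 27.6. It made almost no false selections in the three tabulated columns. With five arms and d=.24, however, it chose the interaction in 22% of runs under ML, where AIC chose it in 96.1%. Even with the right estimator, the named statistics can disagree, and the plan does not say which one counts.

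**The alternative route.** An F test of condition x time on change scores, ten arms, rejected in 4.6%, 5.1% and 4.5% of null runs at SD 4, 5 and 6, with power at d=.24 of 86.0%, 85.0% and 85.5%. It holds its level and does not depend on the SD.

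**The case against.** The strongest reply has three parts.

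First, the plan never states the error outright. The comparison rule follows the dose-response series, and no sentence says that REML deviances will be compared across fixed-effect steps. This is true. But the rule is worded generally, and the sentence after it treats the nested testing as common to the series. On the narrower reading, the REML series has no comparison rule and the dose-response comparisons have no stated estimator. The same wording closes either gap.

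Second, a comparison over 4 or 9 parameters cannot say which app works. App-level coefficients must do that, and they are sound under REML. This also stands, and it limits the consequence: if coefficient tests decide, the app conclusions are unaffected. The plan does not say that they decide.

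Third, the simulated rates rest on assumptions. The plan adds a random time component, which two waves cannot separate from the random intercept and residual variance, and it expects retention of 80 to 100%; the simulation has neither a random slope nor dropout. The correlation matters as well. With ten arms, SD 5 and 0/1 coding, null AIC selection under REML against ML is 23.9% v 3.7% at r .5, 5.5% v 3.4% at r .7, 3.7% v 3.6% at r .75 and 1.7% v 3.1% at r .8. So the inflation under 0/1 coding vanishes near r .75. The dependence on time coding does not: at r .75 and d=.24, AIC chooses the interaction in 97.2% of runs under ML and 29.0% under REML with time 0/4. The exact shifts need none of these assumptions. The d=.24 is also borrowed: the plan states it for main-effect comparisons between two conditions, not for condition x time.

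**Conclusion.** The concern holds and should be fixed before analysis. On the natural reading, following the plan's rule gives invalid comparisons at the condition and condition x time steps. The exact part is the unit dependence: 12.48 (ten arms) or 5.55 (five arms) for doubling the outcome and, in the form omitting log|X'X|, 24.95 or 11.09 for the time unit, against AIC thresholds of 18 and 8. The selection rates only illustrate what this can do. They depend on SD, correlation, number of arms, time coding and REML form, and they are not a forecast for this trial.

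Confidence is medium, because the scope of the rule is inferred and because the effect on Question 3 depends on whether the deviance comparisons or coefficient tests decide.

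**What to change.** State the estimator for every comparison that changes fixed effects, and name the test that decides. Either of two routes is enough:

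- Compare such models by full ML on the same records. Use a likelihood-ratio test for nested steps, with degrees of freedom equal to the number of added fixed-effect parameters, and ML-based AIC or BIC otherwise. The fourth dose-response model, as listed, drops the condition terms and so is not nested above the third; it needs the latter.
- Or prespecify an F or Wald test of condition and of condition x time from the REML fit, with its significance level.

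Say which route decides, and treat the remaining statistics as supporting. Keep REML for random-effect steps with identical fixed effects and for the final estimates and standard errors. The cost is one or two sentences in the SAP and one estimation option, with no effect on data or sample size.
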